9. STATISTICAL ANALYSIS PLAN

9.1. General Statistical Approach

Continuous variables will be summarized using descriptive statistics such as mean, standard deviation, median, minimum and maximum. Categorical variables will be summarized by count and percentage. Group comparisons will be assessed using chi-squared or Fisher's exact tests for categorical variables, and an analysis of variance or Kruskal-Wallis tests for continuous variables where appropriate. Adjustment for covariates listed in Tables 2 and 3 will be explored for each analysis as needed to account for potential confounding effects. Time-dependent covariates will be incorporated to capture changes in covariates across time, as necessary. Inclusion of random effects to account for potential clustering of patients treated at the same study site will be explored. Depending on the rate and pattern of missing data, multiple imputation methods may be considered to account for data missing at random or attributable to non-ignorable drop-out [56]. Planned study outcomes are summarized in Table 4.

9.1.1. Aim 1

Mixed effects regression models will be utilized to assess changes in HRQoL and symptoms within and between groups (i.e.: different treatment regimens) over time. Random effects will be employed to account for the longitudinally correlated nature of repeated questionnaire measurements. Should completion of questionnaires deviate from the planned assessment time points, a spatial power covariance structure will be included to account for the unequal time spacing between assessments within a patient.

9.1.2. Aim 2

Multinomial logistic regression models will be used to identify which patient, clinical, and tumor characteristics (Table 2), and patient attitudes and beliefs (Table 3) influence selection of treatment regimens for each line of treatment. The conditional Cox regression model proposed by Prentice, Williams, and Peterson (PWP) will be used to simultaneously model the gap times between initial diagnosis and first progression and between subsequent progressions as a function of the prognostic factors of interest for progression-free survival. The baseline hazard is expected to differ for first-line therapy and for subsequent lines of therapy, thus event-specific estimates will be obtained. A robust sandwich estimator will be used to account for potential dependencies within patients. Overall survival will be evaluated using a Cox regression model.

9.1.3. Aim 3

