9.2. Sample Size and Power

For this prospective analysis we will have an estimated sample size of 3,010 patients. The sample size is computed for the population with minimum representation in the total sample. 2019 rates of PRRT were 15% in this population. Using a conservative estimation of 10% PRRT administration, and erring on the side of caution, our sample size and power justification is based on approximately 300 subjects (excluding HRQoL questionnaire completion rates). By the law of the minimum, all other treatment subgroups with representation above 10% will yield greater sample size and consequently higher powers for the below-stated differences

9.2.1. Aim 1

The primary objective of Aim 1 is to evaluate changes in HRQoL over time for each treatment. Calculations are based on using the EORTC QLQ-C30 as the primary HRQoL measure. Conservatively

estimating PRRT to be administered in 10% of patients and further expecting a response rate of 60% in the study, we would expect the PRRT group may have approximately 180 patients with complete HRQoL data. Using a repeated measures design with 1 within-subject factor (time: baseline, 6 months, 12 months, and 18 months), the design achieves the following power (Table 5) to detect a time effect for the corresponding mean change. Calculations are based on assuming an autocorrelation of 0.5 between measurements, a standard deviation of 18, and using a Wilks' Lambda Approximate F Test with a 5% significance level. The power will be higher if PRRT administration amounts to more than 10% of the prospective population.

Table 5: Alternative power for changes in EORTC QLQ-C30 within PRRT treated subgroup

MEAN CHANGE IN HRQOL OUTCOMES AT BASELINE, 6, 12 AND 18 MONTHS (RANGE 0-100)*	DIFFERENCE IN MEAN HRQOL SCORE (OVER EACH TIME POINT)	POWER*
65, 62, 59, 56	3-3-3	100%
65, 63, 61, 59	2-2-2	98.3%
65, 63.5, 62, 60.5	1.5-1.5-1.5	84.3%

* THE POWER APPLIES EQUALLY TO POSITIVE OR NEGATIVE SCORING SCALES.

9.2.2. Aim 2

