autocorrelation of 0.5 from one time point to the next and a standard deviation of 5 mL/min/1.73m². Should the standard deviation become unreasonably high in the order of 15 mL/min/1.73m², our sample size is large enough to achieve 99% power under the same parameter settings. In order to test Bonferroni-corrected pairwise differences, the individual tests will achieve 99.6% power to detect a clearance loss of 2 mL/min/1.73m² between two time points. The Bonferroni-corrected tests will be set at a significance level of 0.05/6.

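### Table 5's power matches a constant correlation of 0.5 between all pairs of surveys, but the text words the assumption as an autocorrelation; read as lag-1, the same inputs give about 99%, 81% and 54%

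*Protocol*

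**What the plan says.** Protocol section 9.2.1 plans Aim 1 on the PRRT subgroup: "we would expect the PRRT group may have approximately 180 patients with complete HRQoL data". The design is described as "Using a repeated measures design with 1 within-subject factor (time: baseline, 6 months, 12 months, and 18 months", tested by Wilks' "Lambda Approximate F Test with a 5% significance level". On variability and dependence it says: "Calculations are based on assuming an autocorrelation of 0.5 between measurements, a standard deviation of 18". Table 5 then gives three mean patterns. Steps of 3 points per survey have 100% power, steps of 2 points 98.3%, and steps of 1.5 points ("65, 63.5, 62, 60.5") 84.3%. Table 4 marks Aim 1 HRQoL as powered.

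Section 9.2.3 uses the same design, number of patients, test and correlation value for creatinine clearance. There the assumption reads "autocorrelation of 0.5 from one time point to the next". It states 100% power at an SD of 5 and 99% at an SD of 15.

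Section 9.1.1 plans mixed models with random effects. If questionnaires are completed off schedule, "a spatial power covariance structure will be included to account for the unequal time spacing between assessments within a patient".

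**The concern.** An autocorrelation of 0.5 normally describes successive values in a series, with weaker correlation at longer gaps. Section 9.2.3 says this almost outright, since it ties the 0.5 to neighbouring time points. Neither section says that baseline and 18 months are as strongly correlated as two surveys six months apart.

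The difference matters because the planning scenarios are steady declines, in which the largest contrast is between the first and last surveys. A high correlation between those two surveys makes that contrast precise, and a decaying correlation makes it noisier. Constant correlation is therefore the more favourable of the two structures here, although section 9.2 describes its basis as cautious. Section 9.2 also says that larger treatment groups will have higher power for the same differences, so readers will carry these figures over to other regimens.

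**Working it through.** **Inputs.** From section 9.2.1: n = 180, four surveys, SD = 18, correlation value 0.5, Wilks' Lambda F test, alpha 0.05, steps s = 3, 2 and 1.5 points.

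**Formula.** With one group and four repeated measures, Wilks' Lambda is equivalent to Hotelling's T² on the three successive differences. It has an F distribution with 3 and 180 − 3 = 177 degrees of freedom, and the 5% critical value is 2.656. The noncentrality is

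λ = n · d′(CΣC′)⁻¹d,

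where d holds the three steps, C takes successive differences and Σ = 18²R. For equal steps this becomes λ = n · q · s² / SD², where q depends only on the correlation matrix R.

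The centred mean pattern is s × (1.5, 0.5, −0.5, −1.5), in absolute size.
- Constant correlation 0.5: q = (2.25 + 0.25 + 0.25 + 2.25) / (1 − 0.5) = 10.
- Lag-1 correlation 0.5 (0.5, 0.25, 0.125): q = [0.75 × 1.5² + (0.5 − 0.75)² + (−0.5 − 0.25)² + (−1.5 + 0.25)²] / 0.75 = 3.875 / 0.75 = 5.167.

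The lag-1 structure therefore carries 5.167 / 10 = 52% of the noncentrality that constant correlation gives.

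**Reproducing Table 5, then changing only the correlation structure.**

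| Step | Stated | Constant 0.5: λ | Power | Lag-1 0.5: λ | Power |
|---|---|---|---|---|---|
| 3 | 100% | 180 × 10 × 9 / 324 = 50.0 | 100% | 180 × 5.167 × 9 / 324 = 25.8 | 99.4% |
| 2 | 98.3% | 180 × 10 × 4 / 324 = 22.2 | 98.4% | 180 × 5.167 × 4 / 324 = 11.5 | 81.3% |
| 1.5 | 84.3% | 180 × 10 × 2.25 / 324 = 12.5 | 84.8% | 180 × 5.167 × 2.25 / 324 = 6.46 | 54.1% |

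Software differs in whether λ uses n, n − 1 or n − 3. Across these conventions, constant correlation gives 98.2–98.4% and 84.1–84.8% for rows 2 and 3, which brackets the stated values. Lag-1 gives 80.6–81.3% and 53.4–54.2%. Simulation with 8,000 runs per case gives 98.4% and 85.5% under constant correlation, and 81.6% and 53.8% under lag-1.

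**Could another test explain the gap?** Under lag-1 at n = 180, a Greenhouse-Geisser corrected F test gives 92% and 69% for rows 2 and 3, and a linear-trend test gives 92% and 71%. Neither recovers 98.3% and 84.3%.

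**An intermediate structure.** Correlations of 0.5, 0.4 and 0.3 at lags 1, 2 and 3 are an illustrative assumption. They give 99.9%, 91.1% and 67.0%.

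**Section 9.2.3, SD 15, losses of 2, 4 and 6 (s = 2).** Constant correlation: λ = 180 × 10 × 4 / 225 = 32.0, power 99.9%. Lag-1: λ = 180 × 5.167 × 4 / 225 = 16.5, power about 94%. The stated 99% fits the first and not the second. At an SD of 5 both structures give 100%.

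**The case against.** The strongest reply is that section 9.2.1 never states a decaying correlation. It gives one value between measurements, with no lag or order, and one common correlation is a possible reading. That reading reproduces all three rows, so Table 5 may contain no error of calculation. This stands, and it limits the point to wording and disclosure.

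A reader might infer from section 9.1.1 that the protocol commits Aim 1 to a decaying correlation. The text does not support that. The spatial power structure is conditional on off-schedule surveys and concerns the analysis. The sentence before it relies on random effects, and a patient-level random intercept, if that is what is meant, would itself imply constant correlation. The clause is at most weak support for the lag-1 reading.

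The wording in 9.2.3 is better evidence, but it belongs to another outcome and is silent on longer gaps.

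A reader might also infer that Aim 1 is underpowered. That does not follow. Section 7.1 cites 10 points as the accepted minimal important difference for the QLQ-C30, with scale-level values mostly from 5 to 10. The 1.5-point row totals 4.5 points over 18 months, just below that range. The 2-point row (6 points) keeps 81% and the 3-point row (9 points) 99.4%, even under lag-1. Section 9.2 plans on 10% PRRT use against 15% observed in 2019. At 15% and a 60% response, n = 3,010 × 0.15 × 0.60 ≈ 270, and lag-1 power becomes 94.8% and 73.9% for steps of 2 and 1.5 points.

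**Conclusion.** Table 5 matches a constant correlation of 0.5 between all pairs of surveys. The stated assumption, in its ordinary meaning and as section 9.2.3 words it, is a lag-1 correlation, under which the same inputs give about 99%, 81% and 54%. The gap is negligible in row 1, about 17 points in row 2 and about 30 points in row 3. In 9.2.3 it is about 5 points at an SD of 15, and absent at an SD of 5.

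These figures rest on n = 180, an SD of 18 and the Wilks test, as the protocol gives them. Only a few correlation structures were compared, so constant correlation is the standard structure that fits, not provably the only one. The protocol gives no data on how QLQ-C30 scores correlate over 18 months, so neither structure can be called the true one. What holds is that a choice worth up to 30 points of power is unnamed, and that the words used point to the less favourable structure.

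**What to change.** In section 9.2.1, state that Table 5 assumes a constant correlation of 0.5 between every pair of surveys, and add a column with the lag-1 figures (99%, 81%, 54%). If lag-1 was intended, replace rows 2 and 3 with 81% and 54% and show row 1 as 99%. In either case, do not present about 84% power for 1.5-point steps without naming the constant-correlation assumption.

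Make the same clarification in section 9.2.3: name the structure behind the 99% at an SD of 15, and give about 94% as the lag-1 value.

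The cost is a sentence in each section and a few less favourable figures. The design, the sample size and the planned analyses do not change.

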4. STUDY DESIGN

4.1. Time anchors for study cohort

Study Period: 01/01/2019 to 12/31/2023 (5 years, max 60 months follow-up)

Index Date: Date of diagnosis of eligible NET tumor in the study period

Source Data Range: 01/01/2017-12/31/2023 (7 years, includes 2-year look-back period)

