4.2. Inclusion/Exclusion Criteria

To be eligible for this prospective cohort study subjects must meet **all** of the following criteria:

- i. Incident GEP-NET/Lung NET diagnosis*(see [Appendix A](#))
- ii. Diagnosed 01/01/2019-12/31/2023
- iii. No known prior GEP-NET/Lung NET diagnosis
- iv. Aged ≥ 18 years at diagnosis
- v. At least one site encounter within the study period of January 1, 2019 to December 31, 2023

* See [Appendix A](#) for a full list of International Classification of Diseases, Ninth Revision, Clinical Modification (ICD-9-CM), The International Classification of Diseases, Tenth Revision, Clinical Modification (ICD-10-CM) codes used to define a NET diagnosis. This appendix also lists the ICD-O-3 site codes and eligible histology codes for implementation in tumor registry data sources.

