- 3) **Progression-free survival (PFS).** Time to event data will be calculated from the index date (date of diagnosis) to the earliest of disease progression, death from any cause or end of study follow-up (12/31/2023). Acknowledging that patients may have more than one progression over the study period endpoints of median time to first progression (time from initiation of first-line therapy to progression) and time to second progression (time from second-line therapy initiation to progression) will be observed from targeted chart reviews at annual intervals. In collaboration with our clinician group we have discussed the various limitations of the application of the RECIST 1.1 criteria in NETs. These limitations include an overemphasis on tumor progression (given the low proliferation rate of GEP-NETs, monitoring changes in tumor size is suboptimal), and RECIST 1.1 criteria do not reflect overall tumor load or response to therapy in metastatic patients (i.e.: issues with clinical significance of radiologic progressions). Optimizing the management of NET patients therefore requires considering clinical, biological, and pathological aspects of the tumor. We have therefore chosen to categorize disease progression as DISEASE CONTROL (complete or partial response & stable disease), PROGRESSION (with no treatment change), PROGRESSION (with treatment change), and INDETERMINATE. This clinician-anchored approach has been found to be an optimal and valid method (versus RECIST1.1) for evaluating real-world tumor burden endpoints from EMR data [55].
[Time Frame: median time to progression, assessed annually via chart review]
- 4) **Overall Survival (OS).** Time to event data will be calculated from the date of diagnosis (index date) to the date of death from any cause, or end of study follow-up (12/31/2023). Death and vital status (death date, cause of death) will be pulled from the death table, and death cause table in the CDM. This data may be supplemented from site linkage to the social security death index or cancer registry sources (where possible). Given the prospective nature of the study we also have potential for passive surveillance/follow-up with participant/next of kin with information collected on our follow-up questionnaires.
[Time Frame: Up to 5 years]

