The primary objective of Aim 2 is to evaluate the effect of common treatment sequences on progression-free survival. A lack of historical data on the frequency and number of different variations of treatment sequences, and progression-free survival (PFS) differences by treatment and line of treatment coupled with the likelihood treatment sequences will further differ between the 14 sites taking part in this study make *any realistic and meaningful* sample size and power calculations impossible. Analyses for this aim will be exploratory, and will leverage the use of time-varying covariates in combination with the conditional Cox regression model proposed by Prentice, Williams, and Peterson (PWP) as a means of addressing the heterogeneity evidenced in the data. However, to put into perspective potential PFS differences that may be detected between two treatments using purely hypothetical situations, the below table summarizes power achieved for varying combinations of median PFS differences and number of patients per treatment arm. Calculations are based on the following assumptions: 1:1 treatment allocation, 48 months of uniform accrual and 12 months of follow-up, no loss to follow-up or switching treatments, unadjusted for confounders, and using the Lakatos approximation for a two-sided log-rank test with a 5% significance level.

Table 6: Power determination for changes in median PFS

Median PFS		N Per Treatment Arm	Power
Treatment 1	Treatment 2		
12 months	24 months	45	0.79
		50	0.83
24 months	36 months	175	0.80
		190	0.83

9.2.3. Aim 3

The primary objective of Aim 3 is to evaluate renal toxicity associated with the administration of PRRT as measured by creatinine clearance loss over time. We are expecting 2 mL/min/1.73m² annual decline in creatinine clearance based on averaged long-term follow-up with the most common PRRT isotope 177-Lu [34]. The repeated measures design with 180 subjects and 1 within-subject factor (time: baseline, 6 months, 12 months, and 18 months) achieves 100% power to detect creatinine clearance loss of 2 mL/min/1.73m² by 6 months, 4 mL/min/1.73m² by 12 months and 6 mL/min/1.73m² by 18 months, when the Wilks' Lambda approximate F test is used with a significance level of 0.05, and assuming an

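### Table 6 assumes 48 months of accrual plus 12 months of follow-up, but the protocol's dates give 60 months of diagnoses and no minimum PFS follow-up; power on those dates is about 0.73-0.78, not 0.79-0.83

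*Protocol*

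**What the plan says.** Protocol Section 9.2.2 (Aim 2) introduces Table 6 "to put into perspective potential PFS differences that may be detected between two treatments using purely hypothetical situations". The accrual and follow-up inputs are "1:1 treatment allocation, 48 months of uniform accrual and 12 months of follow-up, no loss to follow-up or switching treatments", and power is computed "using the Lakatos approximation for a two-sided log-rank test with a 5% significance level". The first row of each scenario reads "12 months 24 months 45 0.79" and "24 months 36 months 175 0.80" (median 1, median 2, patients per arm, power). The second rows give 0.83 for 50 per arm and 0.83 for 190 per arm.

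The cohort's dates are fixed elsewhere:

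- Section 4.1: "Study Period: 01/01/2019 to 12/31/2023 (5 years, max 60 months follow-up"). The index date is the date of diagnosis. A maximum follow-up is given, but no minimum.
- Section 4.2: eligibility requires "Diagnosed 01/01/2019-12/31/2023".
- Section 7.2, item 3: PFS runs from diagnosis "to the earliest of disease progression, death from any cause or end of study follow-up (12/31/2023").
- Section 6.2: the single chart review that supplies disease status is placed at about December 2023.

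Table 4 marks PFS under Aim 2 as a powered outcome.

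**The concern.** A design with 48 months of accrual and 12 months of further follow-up guarantees every patient at least 12 months of observation. In this cohort that would require the last diagnosis by 12/31/2022. The protocol sets no such limit: the diagnosis window and PFS follow-up close on the same day. Under uniform accrual, one fifth of patients (12 of 60 months) are diagnosed in 2023 and have between 0 and 12 months of PFS follow-up. Shorter follow-up means fewer events and less power for the same number of patients.

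At stake is the accuracy of the protocol's only statement of what PFS difference it could detect, and of the Table 4 entry that rests on it. The total sample size is not at stake, since Table 6 does not determine it.

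**Working it through.** **Inputs.** From Section 9.2.2: two-sided alpha 0.05, 1:1 allocation, uniform accrual, no loss or switching, medians 12 vs 24 months (45 or 50 per arm) and 24 vs 36 months (175 or 190 per arm). From Sections 4.1, 4.2 and 7.2: diagnoses over 60 months, PFS censored on the last day of that window. Assumption: exponential PFS, so the hazard ratios are 12/24 = 0.50 and 24/36 = 0.667.

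**Formulas.** With accrual A, minimum follow-up F and hazard λ = ln 2 / median, the probability that a patient has an observed event is

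P = 1 − [exp(−λF) − exp(−λ(A+F))] / (λA).

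Expected events are d = n(P1 + P2). Lakatos power is Φ(Σ Dᵢγᵢ / √(Σ Dᵢηᵢ) − 1.96), summed over small time intervals. Here Dᵢ is the expected number of events in interval i, φᵢ the ratio of numbers at risk and θ the hazard ratio (treatment 1 to treatment 2), with γᵢ = φᵢθ/(1+φᵢθ) − φᵢ/(1+φᵢ) and ηᵢ = φᵢ/(1+φᵢ)².

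**Step 1: reproduce Table 6 (A = 48, F = 12), then step 2: use the protocol's dates (A = 60, F = 0).**

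| Medians, n per arm | Table 6 | Events, 48+12 | Power, 48+12 | Events, 60+0 | Power, 60+0 |
|---|---|---|---|---|---|
| 12 vs 24, 45 | 0.79 | 65.2 | 0.795 | 56.0 | 0.731 |
| 12 vs 24, 50 | 0.83 | 72.4 | 0.835 | 62.3 | 0.775 |
| 24 vs 36, 175 | 0.80 | 192.4 | 0.801 | 163.1 | 0.733 |
| 24 vs 36, 190 | 0.83 | 208.9 | 0.832 | 177.1 | 0.767 |

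Table 6 reproduces, so its construction is not in doubt. Reading the 12 months as a fixed 12 months per patient gives only 0.53, 0.57, 0.47 and 0.50, which rules that reading out.

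**Hand check by Schoenfeld's formula** for 24 vs 36 months, 175 per arm, power = Φ(√d·|ln HR|/2 − 1.96) with |ln HR| = 0.4055:

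- 48+12: P1 = 0.617, P2 = 0.482, d = 192.4; √192.4 × 0.4055/2 = 2.81; Φ(0.85) = 0.80.
- 60+0: P1 = 0.525, P2 = 0.407, d = 163.1; √163.1 × 0.4055/2 = 2.59; Φ(0.63) = 0.735.

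Events fall by 15% in this row (163.1/192.4 = 0.848) and by 14% with 45 per arm (56.0/65.2 = 0.860). A log-rank simulation with 4,000 runs per row gives 0.788, 0.835, 0.801 and 0.830 at 48+12, and 0.724, 0.767, 0.748 and 0.770 at 60+0.

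**Step 3: patients per arm for 80% power at 60+0.** The first n to reach 0.80 is 54 (12 vs 24 months) and 207 (24 vs 36 months).

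**Step 4: sensitivity to the shape and end of follow-up (Lakatos).**

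| Pattern | 45 | 50 | 175 | 190 |
|---|---|---|---|---|
| Diagnoses effectively end 3 months early (57+3) | 0.75 | 0.79 | 0.75 | 0.79 |
| Diagnoses effectively end 6 months early (54+6) | 0.77 | 0.81 | 0.77 | 0.80 |
| PFS data to 6/30/2024 (60+6) | 0.78 | 0.82 | 0.79 | 0.82 |

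**Step 5: restricting PFS to diagnoses by 12/31/2022.** This restores 48+12 but drops one fifth of patients: 45 becomes 36 per arm and 175 becomes 140. Power is then 0.70 and 0.71, below the 0.73 obtained by keeping everyone.

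**The case against.** The strongest reply is that Section 9.2.2 disowns the table in advance. It says that realistic power calculations are not possible for Aim 2, calls the analyses exploratory and labels the scenarios hypothetical. The same sentence assumes 1:1 allocation, no switching and no confounding, all plainly idealised for an observational cohort. Table 6 also sizes nothing: Section 9.2 justifies the 3,010 patients through a PRRT subgroup of about 300. All of this stands and limits the consequence. It does not remove the contradiction. The medians and arm sizes are hypothetical, but the diagnosis window and the censoring date are fixed by the protocol, and Table 4 relies on Table 6 when it marks PFS as powered.

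A second reply is that 0.73-0.78 is not forced by the dates alone, since it needs enrolled diagnoses to be uniform to the last day. That is fair. Appendix B reports that diagnosis codes lag true diagnosis, that the high-PPV phenotype needs codes more than 30 days apart, and that registry abstraction typically takes 4-6 months. Late-2023 diagnoses may therefore be under-represented, and a range is needed.

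A third reply is that other sections give later data ends: Section 6.1 speaks of records to about 36 months after joining, and Table 8 ends data collection on 6/30/2024. But the PFS definition itself stops at 12/31/2023, and 6/30/2024 would give six months of minimum follow-up, not twelve.

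A reader might infer more than this: that Table 6 is miscalculated, that Aim 2 or the study is too small, or that patients diagnosed in 2023 add almost no events. The documents support none of these. The arithmetic reproduces. Comparators and arm sizes are not yet fixed (Section 8.1), and with 300 per arm the 24 vs 36 month comparison still has power 0.92 at 60+0. Under Table 6's medians, about 28% (median 12), 15% (median 24) and 11% (median 36) of patients followed for 0-12 months would have an event.

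**Conclusion.** The point holds as an inconsistency of inputs, not as a calculation error. Table 6 gives every patient a 12-month minimum follow-up that Sections 4.1, 4.2 and 7.2 do not provide. On the protocol's dates the four power values drop by about 6-7 percentage points and none reaches 80%. This rests on exponential PFS and on diagnoses spread evenly over 60 months, the latter being Table 6's own accrual assumption extended to the full window. If enrolled diagnoses effectively end three to six months early, the loss is about 2-5 points, and two of the four rows reach 80% in the six-month case. Diagnoses weighted towards the end of the window would lose more than the 60+0 figures show. Because the table is illustrative and the aim exploratory, this is a correction that should be made, but it does not threaten the design.

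**What to change.** Do one of the following:

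1. Recompute Table 6 with 60 months of uniform accrual and no added follow-up. Restate power as about 0.73 and 0.78 (45 and 50 per arm) and 0.73 and 0.77 (175 and 190 per arm), or give about 54 and 207 per arm for 80%. State the uniform-diagnosis assumption and the 0.75-0.81 range if late diagnoses are under-represented.
2. Reconcile the PFS censoring date in Section 7.2 with the chart review timing in Section 6.2, the data extract in Section 6.1 and the data-collection milestone in Table 8, then recompute Table 6 from the agreed date.

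Do not rescue the table by limiting the PFS analysis to patients diagnosed by 12/31/2022: that discards data and lowers power to about 0.70-0.71 in the 45 and 175 per arm rows.

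The first option costs one revised table and a sentence, with slightly less favourable figures and no extra patients. The second also requires agreement on a single end date across sections.
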